We also plan to explore the accuracy of D-dimer with a higher (pregnancy-specific) threshold for positivity and evaluate biomarkers that are not currently used but have potential diagnostic value for PE in pregnant and postpartum women. Plasma D-dimers are specific cross-linked fibrin derivatives produced when fibrin is degraded by plasmin, elevated levels indicating thrombolysis. While highly sensitive for VTE, they are insufficiently specific to make a positive diagnosis as they are elevated in other conditions such as the end of pregnancy, pre-eclampsia, infections, malignancy and postoperative states, but given the present diagnostic paradigm, the potential importance of an exclusionary test that reduces the need for imaging is clear. There is some evidence that using a higher threshold for positivity can improve D-dimer specificity in pregnancy without compromising sensitivity (Chan 2010).

We have conducted a literature search on potential biomarkers both in and outside of pregnancy and also utilised our experts understanding of the pathophysiology of PE. We plan to measure the following biomarkers in addition to D-dimer: cardiac troponin I, B-type natriuretic peptide, prothrombin fragment 1+2, plasmin-antiplasmin complexes, prothrombin time, activated partial thromboplastin time (APTT) and Clauss fibrinogen levels.

Target population

Diagnosed PE: The UKOSS research platform will be used to identify 150 pregnant or postpartum woman diagnosed with PE in the UK after presentation with suspected PE.

Suspected PE: We will recruit 325 pregnant or postpartum women (anticipated 163 pregnant and 162 postpartum) presenting with suspected PE across 11 participating hospitals. We anticipate that 98% (N~319) will have no confirmed diagnosis of PE and will constitute the control group. Those with a diagnosis of PE confirmed (N~6) will be analysed with the cases.

Setting/context

Diagnosed PE: UKOSS collects data from all UK hospitals with a consultant-led maternity unit. The cases may present to the health service through a variety of routes, depending upon local practice, but will ultimately be the responsibility of the obstetric services, and thus women who have a PE at any gestation will ultimately be identified whatever their route of presentation provided their pregnancy is ongoing.

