Suspected PE: Pregnant and postpartum women with suspected PE are investigated in secondary care but may follow a variety of different pathways depending upon local practice. The eight participating hospitals will be selected to reflect this variation but in each case recruitment will be targeted at the location at which the decision to undertake diagnostic imaging is made, whether that is the emergency department, medical assessment unit or maternity unit.

Health technologies being assessed

We will assess health technologies that can be used to select pregnant or postpartum women with suspected PE for diagnostic imaging. This will include technologies validated for use in the non-pregnant population with suspected PE (the Wells criteria, Geneva score, PERC rule and D-dimer) and clinical variables known to predict PE in pregnant or postpartum women. Our initial literature review for this study has identified a number of potential clinical variables, biomarkers and clinical prediction rules that could be used to select women for diagnostic imaging (see table 2).

Table 2: Potential clinical predictors and biomarkers for PE in pregnant and postpartum women

Variable	Source
Age	2,3
Body mass index	2
Parity	2
Previous DVT or PE	2,3
Complications of pregnancy (pre-eclampsia, haemorrhage, diabetes, hyperemesis)	2
Co-morbidities (varicose veins, cardiac disease, hypertension)	2
Hospital admission	2
Recent surgery or immobilization	3
Malignancy	3
Heart rate	3
Clinical signs of DVT	3
Haemoptysis	3
Oxygen saturation	1
D-dimer D-dimer	1,3

^{1:} Diagnostic studies of suspected PE in pregnancy (see table 1)

^{2:} Studies predicting risk factors for developing PE in pregnancy (Knight 2008, Kane 2013, Henriksson 2013, Sultan 2013)

^{3:} Wells, Geneva and PERC clinical prediction scores for suspected PE in non-pregnant patients

We will conduct this trial in compliance with the protocol and GCP requirements

2. Aims and objectives

This study aims to (a) estimate the diagnostic accuracy, effectiveness and costeffectiveness of strategies (including clinical prediction rules) for selecting pregnant or postpartum women with suspected PE for imaging, and (b) determine the feasibility and value of information of further prospective research.

Specific objectives:

- 1. To estimate the sensitivity of clinical variables, existing prediction rules (Wells, Geneva and PERC) and D-dimer for PE diagnosed in pregnant women

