- To estimate the specificity of clinical variables, existing prediction rules and Ddimer in pregnant and postpartum women with suspected PE but negative diagnostic imaging
- 3. To develop a new clinical prediction rule or modify an existing rule to achieve optimal sensitivity and specificity
- 4. To explore the potential diagnostic value of alternative biomarkers for VTE in pregnant and postpartum women and explore the use of D-dimer with a pregnancy-specific threshold for positivity
- 5. To determine the feasibility of using a prospective cohort design to validate a new clinical prediction rule or biomarker
- 6. To estimate the effectiveness of different strategies, in terms of adverse outcomes from thromboembolism, bleeding and radiation exposure, and cost effectiveness, measured as the incremental cost per quality-adjusted life year (QALY)
- 7. To estimate the value of information associated with further research

3. Study Design

The project comprises three main elements and will take 30 months to complete: (1) A case control study (2) A biomarker study. (3) Decision-analysis modelling of effectiveness, cost-effectiveness and value of information In addition, the recruitment rate to the prospective part of the case control study will be used to determine the feasibility of a future cohort study.

[figure not shown]

Figure 1: Summary of the processes and outputs of the project

3.1 A case-control study will address objectives 1-3 above. Cases will be women with diagnosed PE who are retrospectively identified through UKOSS, a UK-wide obstetric surveillance system that has been set up to conduct research on uncommon disorders of pregnancy. This method has been used successfully in a previous study and full details of the UKOSS methods are available at https://www.npeu.ox.ac.uk/ukoss/methodology. Controls will be identified through a prospective study of pregnant or postpartum women presenting to eight hospitals with suspected PE, of whom we anticipate 98% will have no PE diagnosed. Those diagnosed with PE will be analysed as cases.

Why are we not proposing a prospective cohort study?

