3.3 A decision-analysis model will be developed to address objectives 6 and 7. It will estimate the costs incurred and the expected outcomes from thromboembolism, bleeding and radiation exposure if a hypothetical cohort of pregnant or postpartum women were investigated for suspected PE using different strategies with a range of sensitivities and specificities, varying from no testing/treatment to imaging for all. Diagnostic accuracy will be estimated from the case-control study and other parameters from systematic literature reviews. Clinical outcomes will be modelled to estimate the costs and quality-adjusted life years (QALY) accrued by each strategy. From these data, a fully incremental cost-effectiveness analysis will be undertaken. We will estimate the value of information associated with further prospective research. Our research will identify those uncertain parameters that have the most influence on the conclusion and will identify whether any research to narrow the uncertainty in any of these parameters would be deemed cost-effective.

4. Selection and withdrawal of participants

Inclusion Criteria- Diagnosed PE (Cases)

We will identify and collect data from all pregnant and postpartum* women diagnosed with PE, defined as either

- (1) PE confirmed using imaging (angiography, CT, magnetic resonance imaging or ventilation–perfusion scan showing a high probability of PE),
- (2) PE confirmed at surgery or post-mortem
- (3) a clinical diagnosis of PE who received a course of anticoagulation therapy for more than one week.
- *The postpartum period is defined as women within 6 weeks (42 days) of the end of a pregnancy beyond the first trimester

Exclusion criteria-- Diagnosed PE (Cases)

(1) Women with PE identified on asymptomatic screening.

Inclusion Criteria- Suspected PE (Controls)

(1) Any pregnant or postpartum* woman who requires diagnostic imaging for suspected PE (as outlined above, but also including lower limb venous imaging) will be eligible for inclusion.

*The postpartum period is defined as women within 6 weeks (42 days) of the end of a pregnancy beyond the first trimester

Exclusion criteria-- Suspected PE (Controls)

- (1) Women who need life support upon presentation to hospital (including chest compressions and assisted ventilation)
- (2) Women who have been diagnosed with PE earlier in the current pregnancy and are currently receiving treatment
- (3) Women who are unable or unwilling to provide informed consent.

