- (4) Aged <16 years

Inclusion Criteria- Diagnosed DVT

(1) Pregnant, or post-partum (defined as within 6 weeks of the end of a pregnancy beyond the first trimester) with a diagnosis of DVT confirmed by imaging (Ultrasound or venography)

Exclusion criteria- Diagnosed DVT

- (1) Women with suspected PE (who should be included as suspected PE)
- (2) Women who have been diagnosed with PE or DVT earlier in the current pregnancy and are currently receiving treatment
- (3) Women who are unable or unwilling to provide informed consent
- (4) Aged <16 years

Sampling and Informed Consent

Diagnosed PE: The sampling method has been successfully used in a previous study (Knight 2008). Nominated clinicians in each consultant-led maternity unit in the UK will be sent a card each month and asked to report all cases of antenatal or postnatal PE, thus covering the entire cohort of UK births. To ensure all cases are identified, we will independently contact all radiology departments and ask them to report any cases of PE in pregnant women, providing only their year of birth and date of diagnosis. If a case is identified which has not been reported through UKOSS, the relevant UKOSS reporting clinician will be contacted and asked to complete a data collection form. In addition, ascertainment of any maternal deaths from PE occurring during the study period will be checked through MBRRACE-UK, the collaboration responsible for the UK Confidential Enquiries into Maternal Death. Where a case is identified, the UKOSS clinician will be contacted and asked to complete a data collection form if appropriate.

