or a modified rule could outperform existing rules we will develop a new rule from the model variables or modify an existing rule with the aim of achieving the highest specificity at which sensitivity of at least 95% is maintained. The multivariate model will be validated internally using cross-validation, i.e. the data will be split into a training and validation set at random, in the ratio 2:1 and the model fit to the training and tested in the validation test. In addition we will use bootstrapping to validate the model (Royston 2009).

Secondary analyses will explore (a) whether the findings differ between pregnant and postpartum women, and (b) whether findings are sensitive to the inclusion of women with clinically diagnosed PE in the reference standard definition. An additional secondary analysis will test the performance of a clinical decision rule developed through expert consensus. Standard Delphi and Nominal Group methodology will be used with panel membership including obstetric, emergency medicine, haematology, and radiology expertise (Dalkey 1972, Delbecq and Van de Ven 1971). The sensitivity and specificity of the resulting CDR for identifying diagnosed PE will then be determined in the DiPEP cohort.

Further details will be provided in a separate statistical analysis plan.

7. Study supervision

A Steering Committee will be appointed to provide independent oversight. It will consist of SG, the project manager, two patient/public representatives ([name] and [name]) and four independent experts, one of whom will chair the committee.

The study will be managed by a full-time project manager based in the Sheffield CTRU. The CTRU will also provide data management, statistical and health economic support. A Project Management Group consisting of the co-applicants and appointed research staff will undertake day to day management of the study and will meet at least quarterly.

The study Sponsor will be Sheffield Teaching Hospitals NHS Foundation Trust and SG will take overall responsibility for the study.

There will be no Data Monitoring and Ethics Committee (DMEC) required for this study. A data management and monitoring plan will be devised in accordance with the Sheffield CTRU SOP (DM009)

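### Postpartum PE cases are eligible, but the radiology completeness check and Objective 1 cover pregnant women only, and pregnancy status is named only in a secondary analysis

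*Protocol*

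**What the plan says.** On who counts as a case, Section 4 (Inclusion Criteria, Diagnosed PE) is clear: "We will identify and collect data from all pregnant and postpartum* women diagnosed with PE", with postpartum meaning within 42 days of the end of a pregnancy beyond the first trimester.

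Section 4 (Sampling and Informed Consent) gives three routes to cases:

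- The monthly UKOSS card asks clinicians to "report all cases of antenatal or postnatal PE, thus covering the entire cohort of UK births".
- As a completeness check, "we will independently contact all radiology departments and ask them to report any cases of PE in pregnant women".
- Maternal deaths from PE are checked through MBRRACE-UK.

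Other places use a narrower population. Section 1 (Setting/context) says "women who have a PE at any gestation will ultimately be identified whatever their route of presentation provided their pregnancy is ongoing". Objective 1 in Section 2 is "To estimate the sensitivity of clinical variables, existing prediction rules (Wells, Geneva and PERC) and D-dimer for PE diagnosed in pregnant women". The consent paragraph for diagnosed PE in Section 4 describes the aim as collecting confirmed PE cases in pregnancy, with no mention of the postpartum period. Objective 2, by contrast, concerns specificity "in pregnant and postpartum women with suspected PE but negative diagnostic imaging", and the suspected-PE group is "anticipated 163 pregnant and 162 postpartum" (Section 1, Target population).

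In the analysis, pregnancy status is named once: "Secondary analyses will explore (a) whether the findings differ between pregnant and postpartum women" (Section 6, Data Analysis). The association tests and the multivariable model are described without reference to it.

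**The concern.** Section 3.1 defends the case-control design partly on the ground that the cases will be a representative sample of women who present with suspected PE and are diagnosed and treated. That safeguard weakens if one group of cases has a second chance of being found and the other has not. The sampling method is supported by its success in a previous UKOSS study, but Sections 1 and 3.1 describe that study as one of antenatal PE, so its success says nothing about postpartum capture.

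Three things are at stake:

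- **Incidence.** Section 6 uses the case data to estimate incidence in pregnancy and postpartum. Missed postpartum cases lower that estimate directly.
- **Pooled sensitivity.** If sensitivity differs by status, losing postpartum cases pulls the pooled value towards that of pregnant women.
- **Association tests and rule derivation.** Table 2 lists hospital admission, recent surgery or immobilisation, haemorrhage and D-dimer. These plausibly differ between pregnant and postpartum women whether or not PE is present. Without adjustment, such a predictor can appear linked to PE only because the case and control groups have different mixes.

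**Working it through.** **1. The protocol's own case mix.** Inputs from Section 3.1: 723,913 births, 1.3 antenatal and 2.0 combined PE cases per 10,000 maternities.

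- 723,913 × 1.3/10,000 = 94.1 (stated: 94).
- 723,913 × 2.0/10,000 = 144.8 (stated: 145).
- Antenatal share with full capture: 94/145 = 65%.

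The stated counts reproduce. The two rates come from different sources, so 65:35 is approximate. The suspected-PE group is 163/325 = 50.2% pregnant, which is an expectation and not a quota.

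**2. Routes to a case, side by side.**

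- Pregnant, surviving: card, then radiology check.
- Postpartum, surviving: card only.
- Any maternal death from PE: card, then MBRRACE-UK.

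The gap is therefore non-fatal postpartum PE that the card misses. The protocol gives no completeness figure for the card, so the number lost cannot be calculated.

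**3. Assumed loss.** Suppose half of the postpartum cases are missed. The postnatal rate is 2.0 − 1.3 = 0.7 per 10,000, so 0.35 would be observed.

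- Antenatal share: 1.3/(1.3 + 0.35) = 79%.
- Combined incidence observed: 1.65 instead of 2.0, which is 17.5% too low. The postnatal part would be halved.

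**4. A predictor with no link to PE within either group.** Assumed: present in 10% of pregnant and 40% of postpartum women; 156 cases and 319 controls.

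Controls positive: 0.502 × 0.10 + 0.498 × 0.40 = 0.25.

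*At a 65% antenatal share:*
- Cases positive: 0.65 × 0.10 + 0.35 × 0.40 = 0.205.
- OR = (0.205/0.795)/(0.25/0.75) = 0.77.
- SE = √(0.205 × 0.795/156 + 0.25 × 0.75/319) = 0.0404; z = −0.045/0.0404 = −1.11.
- Chance of two-sided p<0.05: about 20%.

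*At a 79% antenatal share:*
- Cases positive: 0.788 × 0.10 + 0.212 × 0.40 = 0.164.
- OR = (0.164/0.836)/(0.25/0.75) = 0.59.
- SE = √(0.164 × 0.836/156 + 0.25 × 0.75/319) = 0.0383; z = −0.086/0.0383 = −2.26.
- Chance of p<0.05: about 62%, or about 57% with the pooled null variance that a chi-square test uses.

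A milder predictor (20% and 30%) gives about 6% at a 65% share and 10–11% at 79%. Other assumed contrasts, at an 80% share, give ORs from 0.53 (5% and 30%) to 0.74 (20% and 40%). The direction is stable; the size depends on the assumptions.

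**5. Pooled sensitivity.** With assumed sensitivities of 95% in pregnant and 85% in postpartum women:

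- At 65:35: 0.65 × 95 + 0.35 × 85 = 91.5%.
- At 79:21: 0.788 × 95 + 0.212 × 85 = 92.9%.

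**6. Precision by stratum.** SE = √(0.9 × 0.1/n) at 90%.

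- Pooled, 150 cases: 2.45%, matching the stated figure of about 2.5%.
- At 65:35: 97.5 pregnant cases give 3.0%, and 52.5 postpartum cases give 4.1%.
- Specificity, about 160 controls per stratum: 2.4%. With about 122 each after attrition: 2.7%.

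**The case against.** The strongest reply is that postpartum cases are plainly inside the design. They are eligible, the main reporting route asks for them every month in every consultant-led unit, and fatal cases have their own check. This stands. A reader might infer that cases are captured mainly in ongoing pregnancy, or that postpartum PE is known to be under-ascertained. The documents do not support either reading. The Setting/context sentence concerns gestation and route of presentation, and it does not say that postnatal cases go unreported. What the text shows is a risk of unknown size.

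A second reply also stands. A 65:35 mix in cases against 50:50 in controls is not bias in itself. If PE risk differs by status, a complete cohort would show different mixes among women with and without PE, and sensitivity and specificity are properly weighted by those respective mixes. It would therefore be wrong to conclude from the mixes alone that the primary accuracy estimates describe different populations, or to reweight sensitivity to the suspected-PE mix. In the example above, a complete 65:35 series correctly gives 91.5%, and reweighting to 50:50 would report 90%.

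Third, only predictors that differ by status are affected, and the larger odds ratio needs two assumptions stacked together. The 319 controls also ignore the attrition of up to 25% allowed for in Section 6. These limits stand.

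Fourth, the model's variable list is open, the protocol defers detail to a separate SAP, and secondary analysis (a) looks at status. This stands in part: a SAP could add the adjustment. It cannot recover cases that were never sought, and it does not settle which population Objective 1 means. The planned sensitivity analysis for design-related bias (Section 5.3) applies a general estimate of case-control overstatement and does not address postpartum capture.

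**Conclusion.** The point holds as an internal inconsistency with a practical consequence. The case definition and the UKOSS card include postpartum women. The radiology check, the Setting/context assurance, Objective 1 and the consent paragraph do not. Followed as written, non-fatal postpartum cases missed by the card have no backup. That creates a risk of differential ascertainment, of understated postpartum incidence and, since no primary analysis is said to account for pregnancy status, of confounded crude tests and rule derivation.

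The size is not computable from the protocol. At its own implied 65% antenatal share, the illustrative null predictor shows a modest distortion (OR 0.77, about a 20% chance of p<0.05). The larger figures (OR 0.59, 57–62%) rest on the assumption that half the postpartum cases are missed. All of them rest on the assumed 10% and 40% prevalences. The changes are worth making because they cost little, not because a large bias has been shown.

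**What to change.** - Word the radiology request to cover PE in women who are pregnant or within 42 days postpartum. The protocol footer is dated March 2016, inside the planned collection period (April 2015 to September 2016), so the request may have to be made retrospectively. It needs only year of birth and date of diagnosis.
- Align Objective 1, the Setting/context sentence and the consent paragraph with the Section 4 case definition.
- Include pregnant/postpartum status in the multivariable model and stratify the association tests by it.
- Report sensitivity and specificity within each stratum beside the pooled values. Leave pooled sensitivity weighted by the mix among women with PE, and pooled specificity by the mix among women without PE.

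The cost is one phrase in the radiology request, some further reports to follow up, and short analysis wording; pregnancy status needs no new data item. Stratum-specific intervals are wider: at 65:35 the SE of sensitivity is about 3.0% in pregnant and 4.1% in postpartum women, against 2.45% pooled. One practical limit, as a matter of judgement, is that radiology records may show pregnancy more reliably than recent delivery, so the extended check may narrow the gap without closing it.

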5.1 Data Collection Procedure

5.1.1 Diagnosed PE

Clinicians who report a case will be asked to complete a data collection form detailing potential predictor variables, diagnostic test results, management and outcomes. Up to five reminders will be sent if completed forms are not returned. All data requested will be anonymous. On receipt of data collection forms, cases will be checked to confirm that they meet the case definition. Duplicate reports will be identified by comparing the woman's year of birth, hospital and expected date of delivery.

Collection of data on cases in this way means we are not able to alter hospital diagnostic/testing practice. Thus, to help ensure maximal information is available on diagnostic tests such as D-dimers, the information provided to UKOSS clinicians in advance of the study will highlight the relevant sections of RCOG and ESC guidance about diagnostic testing. This current guidance suggests that D-dimer testing is helpful to exclude PE, although not helpful as a marker of positivity. We will, in addition, provide staff with information about the other biomarkers of interest, and ask them to record the results of these tests if they are undertaken as part of hospital standard practice. We will monitor the completeness of data provision on diagnostic testing throughout the data collection period.

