PE is a leading cause of death in pregnancy and postpartum that affects women who would otherwise expect to have long life expectancy in full health. Furthermore, the outcome for the fetus is dependent on the outcome for the mother. Patients with appropriately diagnosed and treated PE have a low risk of adverse outcome, so accurate diagnosis can result in substantial benefits. However, the investigations used to diagnose PE (diagnostic imaging with VQ scanning or CT pulmonary angiography) carry risks of radiation exposure, reaction to contrast media and false positive diagnosis, are inconvenient for patients and incur costs for the health services. Clinicians therefore face a difficult choice when deciding how to investigate suspected PE in pregnant and postpartum women, between risking the potentially catastrophic consequences of missed diagnosis if imaging is withheld and risking iatrogenic harm to women without PE if imaging is over-used.

Current practice

Guidelines from the Royal College of Obstetricians and Gynaecologists (2010) and American Thoracic Society (Leung 2011) recommend that pregnant or postpartum women with suspected PE should all receive diagnostic imaging, while guidelines from the European Society of Cardiology (Torbicki 2008) suggest a possible role for D-dimer in selecting patients. Current data suggest that use of an unselective approach is resulting in a low prevalence of PE among those investigated. The most recent studies of suspected PE in pregnancy report prevalence of between 1.4 and 4.2% (Bourjeilly 2012, Abele 2013, Nijkeuter 2013, Cutts 2014), while audit data from Sheffield Teaching Hospitals NHS Foundation Trust show a prevalence of 2% among those undergoing imaging. We therefore appear to be exposing 50 women (and foetuses in pregnant women) to the risks of diagnostic imaging for every one with PE who is able to benefit from diagnosis and treatment.

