If we assume that the ratio of cases to controls is about 0.4, then this sample size is sufficient to identify an odds ratio of a clinical predictor of about 2, with 90% power and 5% two sided significance (Machin 2009).

Data Analysis

Women with PE who did not present with suspected PE prior to diagnosis, i.e. those who need life support upon presentation to hospital (including chest compressions and ventilator support) will be excluded from primary and secondary analyses, but their data used to estimate key parameters, such as incidence of PE in pregnancy and postpartum.

Two independent assessors, blind to clinical predictors and blood results, will classify participants as having PE using diagnostic imaging results, details of adverse events and details of treatments given. Disagreements will be resolved through adjudication by a third assessor. Women with a clinical diagnosis of PE based on imaging evidence of DVT will be analysed as cases. Women with a purely clinical diagnosis of PE (i.e. without any imaging evidence of DVT or PE) will be excluded from primary analysis but included as cases in secondary analysis. Women with clinically ruled out PE (i.e. suspected PE without diagnostic imaging for PE) will be excluded from the primary analysis but included as controls in secondary analysis.

Women with multiple presentations i.e. classified as having a PE in the Suspected PE group and also identified through UKOSS, will be cross referenced using the date of the PE and the woman's year of birth to ensure that case is only used once in the analysis. Similarly, for the biomarker study, women collected as a Diagnosed DVT and then also included as a Suspected PE will also cross referenced and their blood samples will be highlighted as being from the same individual.

Sensitivity, specificity, likelihood ratios and/or c-statistics will be estimated with a 95% confidence interval for clinical predictors, biomarkers and existing prediction rules (Wells, Geneva and PERC) using data from cases and controls. Chi-square or Fisher's Exact tests will be used to test the association between PE diagnosis and each clinical variables, D-dimer (dichotomised at the standard threshold) and prediction rule. Multivariate analysis will then be used to identify which variables are independent predictors of PE. If the multivariate model suggests that a new combination of variables

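### Primary D-dimer accuracy depends on a decision to image that D-dimer may itself influence, so sensitivity is at risk of upward and specificity of downward bias

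*Protocol*

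**What the plan says.** Section 4 of the protocol admits as a control "Any pregnant or postpartum* woman who requires diagnostic imaging for suspected PE". The Data Analysis part of section 6 then narrows the primary analysis on both sides. For controls: "Women with clinically ruled out PE (i.e. suspected PE without diagnostic imaging for PE) will be excluded from the primary analysis". For cases: "Women with a purely clinical diagnosis of PE (i.e. without any imaging evidence of DVT or PE) will be excluded from primary analysis". Both groups return only in secondary analysis. A clinical diagnosis supported by imaging evidence of DVT still counts as a case. The case definition also has one route without imaging that the primary analysis keeps, namely "PE confirmed at surgery or post-mortem".

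Section 5.1.2 leaves imaging to local protocols. Section 5.1.1 says the study cannot change hospital testing practice. To obtain as much D-dimer data as possible, it plans to draw the attention of UKOSS clinicians, before the study starts, to parts of the RCOG and ESC guidance, which it summarises thus: "This current guidance suggests that D-dimer testing is helpful to exclude PE, although not helpful as a marker of positivity".

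The Introduction (Current practice) says that the RCOG and American Thoracic Society guidelines "recommend that pregnant or postpartum women with suspected PE should all receive diagnostic imaging". It credits the ESC guideline only with suggesting that D-dimer may have a role in selecting patients.

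**The concern.** A test's accuracy is distorted when its result affects who receives the reference standard. A woman with PE and a negative D-dimer who is not imaged will usually not be counted as a case. A woman without PE and with a negative D-dimer who is not imaged will not be a primary control. The first loss raises apparent sensitivity and the second lowers apparent specificity.

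Objectives 1 and 2 include D-dimer sensitivity and specificity, and the protocol's Publication section foresees that D-dimer might prove able to rule out PE. The decision model discharges test-negative women without treatment, so an inflated sensitivity understates missed PE. The protocol does not name this mechanism. It also sends a rule-out message about the test under evaluation to the clinicians who report about 150 of the roughly 155 cases.

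**Working it through.** **The plan's own figures.** Section 6 states standard errors of about 2.5% for sensitivity and 2.0% for specificity at a true value of 90%. With SE = √(p(1−p)/n):

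- n = 150: √(0.9 × 0.1/150) = 2.45%
- n = 250: √(0.9 × 0.1/250) = 1.90%

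Both reproduce. They describe sampling error only, and the first assumes that every case has a D-dimer result.

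**Effect of D-dimer-dependent imaging.** Let v be the chance of imaging after a negative D-dimer divided by the chance after a positive one. The protocol gives no value for v, so a range is shown. The true values of 90% and 40% are also illustrative.

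- Apparent sensitivity = s / (s + (1 − s)v)
- Apparent specificity = sp·v / (sp·v + 1 − sp)

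| v | Sensitivity, true 90% | Bias, points | Bias ÷ 2.45 | Specificity, true 40% |
|---|---|---|---|---|
| 1 | 90.0% | 0 | 0 | 40.0% |
| 0.9 | 90.9% | 0.9 | 0.4 | 37.5% |
| 0.75 | 92.3% | 2.3 | 0.9 | 33.3% |
| 0.5 | 94.7% | 4.7 | 1.9 | 25.0% |
| 0.25 | 97.3% | 7.3 | 3.0 | 14.3% |

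For v = 0.5: 0.90/(0.90 + 0.10 × 0.5) = 0.947, and 0.40 × 0.5/(0.40 × 0.5 + 0.60) = 0.25.

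**Recapture.** These formulas assume that a PE missed after a negative D-dimer never enters later. If a fraction r does enter, with the negative result recorded, v for cases becomes v + (1 − v)r. With v = 0.5 and r = 0.5 (both assumed) this is 0.75, and apparent sensitivity is 92.3% rather than 94.7%.

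**Existing safeguards.**

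- Blinded classification (section 6) acts after women have been selected for imaging.
- The radiology check (section 4) finds only imaged women. The maternal-death check finds only fatal PE.
- The data on non-recruited women (5.1.3) cover those who were eligible, hence already judged to need imaging.
- The design rationale (section 3.1) aims for controls representative of women with negative imaging, which is itself conditional on imaging.
- The adjustment in 5.3 applies a published estimate of case-control bias to sensitivity. It is not described as covering imaging that depends on D-dimer, and it leaves specificity unchanged.

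**The two accounts of the guidance.** Section 5.1.1 attributes the helpful-to-exclude view to RCOG and ESC guidance together. The Introduction attributes imaging of all women to the RCOG and only a possible D-dimer role to the ESC. This conflict needs no assumption about v.

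**The case against.** The strongest reply is that v may be close to 1. The Introduction describes an unselective approach with about 2% prevalence among women imaged, and under such practice there is no bias. This stands: the size cannot be derived from the protocol.

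Several stronger readings are tempting but not supported.

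- A reader might infer that D-dimer accuracy is estimated only in imaged women and that such PE can never become a case. The surgery and post-mortem route, the secondary analyses, re-presentation and the death check show otherwise.
- A reader might infer that a poor D-dimer could falsely reach the plan's 95% sensitivity target. In section 6 that target belongs to a new or modified prediction rule, not to D-dimer alone.
- A reader might infer that the UKOSS figure drives every D-dimer strategy in the model. Section 5.3 takes biomarker sensitivities from about 25 women in the biomarker study, which excludes UKOSS cases (5.2). Results from those study samples are withheld from carers (section 9), so they cannot themselves determine imaging. Some risk remains, because the women with suspected PE in that study are still recruited around imaging and the model's specificities come from women with negative imaging.
- A reader might infer that the clinician information certainly causes selection. Its stated aim is complete data, and its recipients are maternity-unit reporters who may not make the imaging decision. It may strengthen the selection; the protocol does not show that it does.

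The protocol also acknowledges case-control bias and plans to vary accuracy in the model. A specific analysis may exist in the separate statistical analysis plan, which was not available here.

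**Conclusion.** The concern holds as a conditional risk in the primary analysis. The direction follows from the entry rules whenever a negative D-dimer makes imaging less likely. The size depends on v, which is unknown: zero at v = 1, about one planned standard error of sensitivity at v = 0.75, and about two at v = 0.5, where 90% appears as 94.7%. Specificity moves the other way, from 40% to 25% at v = 0.5. These figures assume that v is the same with and without PE and that missed cases do not re-enter. That D-dimer sensitivity is in fact biased upward would be more than the protocol supports. The disagreement between 5.1.1 and the Introduction about the guidance stands regardless.

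**What to change.** 1. Reconcile section 5.1.1 with the Introduction on what the RCOG and ESC guidance says. Limit the information to UKOSS clinicians to a neutral request to record D-dimer results. Material already sent can be followed by a correction.
2. Where still possible, add one item to the case and control forms: was a D-dimer result known before the decision to image?
3. Keep the primary D-dimer estimate. Add a verification-bias sensitivity analysis of both sensitivity and specificity over a stated range of v, starting at v = 1, and carry it into the decision model for strategies that use D-dimer.
4. State in the report that the unadjusted sensitivity may be an upper bound.

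I would not restrict the primary estimate to women whose imaging was judged uninfluenced by D-dimer. That judgement would be made retrospectively, and women imaged despite a negative result would tend to be coded as uninfluenced, which could bias sensitivity downward and lose cases.

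The cost is one form item and some extra analysis. This version is dated 2 March 2016 and UKOSS collection was planned from 1 April 2015 to 30 September 2016, so the new item will be incomplete for cases already reported. A neutral message may also lead to fewer D-dimer tests being ordered.
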